2. SYNOPSIS

Name of Sponsor/Company:

Sage Therapeutics, Inc. (hereafter referred to as Sage Therapeutics, or Sage)

Name of Investigational Product:

Brexanolone

Name of Active Ingredient:

Brexanolone (USAN/INN), also known as allopregnanolone (scientific name)

Protocol Number: 547-TRM-201

IND Number: 162652

Title of Study:

An Open-Label Study Evaluating the Safety, Tolerability, Pharmacokinetics, and Efficacy of Brexanolone in the Treatment of Adult Participants with Tinnitus

Short Title: An Open-Label Study Evaluating Brexanolone in Adults with Tinnitus

Number of Sites and Study Location: This study will take place at a 1 to 2 sites in the US.

Phase of Development: 2

Planned Duration for Each Study Participant:

Each participant's involvement is up to 35 days, including a maximum 28-day Screening Period, a 1-day Clinic Treatment Visit, and a 6-day Follow-up Period.

[figure not shown]
Objectives and Endpoints:

	Endpoints	Objectives
		Primary
iverse	• Incidence of treatment-emergent advers events (TEAEs)	To evaluate the safety and tolerability of brexanolone
		Secondary
infusion	 Change from baseline to Hour 6 of infus in VAS loudness (VAS-L) ratings Change from baseline to Hour 6 of infus in VAS annoyance (VAS-A) ratings 	To assess subjective tinnitus perception during brexanolone infusion based on Visual Analog Scales (VAS)
diary over	 Change from baseline to post-infusion in VAS-L ratings measured via daily diary multiple days Change from baseline to post-infusion in VAS-A ratings measured via daily diary over multiple days 	To assess subjective tinnitus perception after brexanolone infusion based on VAS
in io di	 in VAS loudness (VAS-L) ratings Change from baseline to Hour 6 of in in VAS annoyance (VAS-A) ratings Change from baseline to post-infusio VAS-L ratings measured via daily dimultiple days Change from baseline to post-infusio VAS-A ratings measured via daily di 	To assess subjective tinnitus perception during brexanolone infusion based on Visual Analog Scales (VAS) To assess subjective tinnitus perception

 Change from baseline in vital signs, electrocardiogram (ECG), and clinical laboratory parameters

Study Description:

This is an open-label study to evaluate the safety, tolerability, , and efficacy of brexanolone in adults with tinnitus following a single 6-hour continuous intravenous (IV) infusion. The study design is presented in Figure 1.

This study includes a Screening Period of up to 28 days, a 1-day Treatment Period, and a 6-day Follow-up Period. After providing informed consent, participants will undergo screening assessments as outlined in Table 2 to determine eligibility.

Screening Period:

The Screening Period begins with the signing of the informed consent form (ICF). Eligible participants will complete additional eligibility and baseline assessments as specified in the Schedule of Assessments (Table 2).

Starting 7 days before administration of investigational product (IP) (Day -7), participants will have twice daily remote predose assessments as indicated in Table 2. Participants will receive training on how to perform all remote assessments during Screening. The participant will be contacted by the site on Day -7 through Day -1 to remind them to begin remote assessments. Assessments will be performed remotely by the participant on Day -7 through Day -1. Ratings for both VAS-L and VAS-A will be done twice daily, once each in the morning and evening.

Participants will be excluded from dosing if they do not successfully perform at least 10 of the 14 remote VAS assessments.

Treatment Period:

A continuous, 6-hour IV infusion of IP will be administered at the Clinic Treatment Visit on Day 1. Assessments will be performed as indicated in Table 3.

The participant will spend approximately 9 hours in the clinic on Day 1: 1 hour for setup of IV pump and assessments performed prior to administration of IP, 6 hours for the IP infusion, and 2 hours for safety observation at the conclusion of the IP infusion. At the discretion of the investigator, participants may stay in the clinic overnight after the end of infusion.

Due to the risk of excessive sedation and sudden loss of consciousness, for the duration of the infusion, participants will be monitored for hypoxia using continuous pulse oximetry equipped with an alarm and will be assessed for excessive sedation by a healthcare provider. If excessive sedation occurs at any time during the infusion, the infusion will be stopped until the symptoms resolve. The infusion may be resumed at the same or lower dose per protocol guidance. The infusion will be immediately stopped if pulse oximetry reveals hypoxia,

specifically if this occurs in the context of excessive sedation or sudden loss of consciousness. After an episode of confirmed hypoxia, the infusion should not be resumed.

For lactating subjects, the investigator and subject should weigh the developmental and health benefits of breastfeeding during the infusion against any potential adverse effects on the breastfed child from brexanolone or from the underlying maternal condition. Subjects may continue to breastfeed or express milk to feed their infant during the infusion if the benefit is deemed to outweigh the risk. During the study, a qualified lactation consultant will be made available to subjects upon request.

In this study, excessive sedation, loss of consciousness, and any sedation-related AE that leads to dose reduction, interruption, or termination will be recorded as an adverse event of special interest (AESI).

A fall precaution protocol must be in place for the duration of the brexanolone infusion.

At the conclusion of the IP infusion, if deemed medically appropriate by the investigator, participants will be released from the clinic after the 2-hour safety observation period and completion of assessments. Participants will be cautioned against engaging in potentially hazardous activities requiring mental alertness, including driving, until any sedative effects have dissipated. A designated companion must drive the participant when they are discharged from the clinic.

Follow-Up Period:

Assessments for the Follow-up Period will be performed as indicated in Table 3. The participant will be contacted by the site on Day 2 through Day 6 to remind them to begin remote assessments. Follow-up assessments will be conducted remotely on Day 2 through Day 6. Ratings for both VAS-L and VAS-A will be done twice daily, once each in the morning and evening.

Participants will return to the clinic approximately 6 days after the last dose of IP (Day 7 ± 1 day) for efficacy and safety monitoring. The EOS Visit will be conducted at the time of discontinuation if this occurs at any time before Day 7 ± 1 day (see Section 8.4.2).

Number of Participants (planned): Up to 24 participants will be dosed to achieve approximately 20 study completers, assuming a 20% study discontinuation rate among dosed participants.

Eligibility Criteria:

Inclusion Criteria:

Participants must meet all of the following criteria to qualify for participation in this study:

- 1. Participant has signed an ICF before any study-specific procedure is started.
- 2. Participant is ambulatory and is 18 to 65 years of age, inclusive, at the time informed consent is obtained.
- 3. Participant has a designated companion for the Clinic Treatment Visit who will drive them when they leave the clinic.
- 4. Participant is in good physical health and has no clinically significant findings (excluding tinnitus), as determined by the investigator on medical history and physical examination, including neurologic and mental status examinations, 12-lead ECG, or clinical laboratory tests.
- 5. Participant has a diagnosis of subjective, idiopathic, unilateral or bilateral, non-pulsatile tinnitus (eg, not due to medical disease) of ≥ 6 months and ≤ 10 years duration.
- 6. Participant has mild to severe tinnitus distress according to Tinnitus Handicap Inventory (THI) score of 24 to 68 at Screening.
- 7. Participant is willing and able to safely discontinue the use of central nervous system (CNS) depressants (eg, opioids and benzodiazepines), antidepressants, anticonvulsants, CNS stimulants (with the exception of caffeine), aspirin, other nonsteroidal anti-inflammatory drugs, and

- aminoglycosides at least 14 days or 5 half-lives (whichever is longer) prior to receiving IP and through completion of the study.
- 8. Female participant agrees to use at least one method of highly effective contraception during participation in the study and for 30 days following the last dose of IP, unless she is postmenopausal, permanently sterile, or does not engage in sexual relations which carry a risk of pregnancy (see Section 9.2.5).
- 9. Male participant with a partner who is of childbearing potential agrees to use an acceptable method of effective contraception for the duration of the study and for 13 weeks after receiving the IP, unless the participant does not engage in sexual relation(s) which carry a risk of pregnancy in his female partner(s). Acceptable methods of effective contraception are listed in Section 9.2.5.
- 10. Male participant is willing to abstain from sperm donation for the duration of the study and for 13 weeks after receiving the IP.

Exclusion Criteria:

Participants who meet any of the following criteria are disqualified from participation in this study:

- 1. Participant has history or presence of any neurologic disease or condition, including, but not limited to, unexplained loss of consciousness, seizure disorder including a prior nonfebrile seizure, and closed head trauma with clinically significant sequelae.
- 2. Participant has a history of sleep apnea or any clinically significant respiratory conditions that may predispose the participant to hypoxia during the infusion.
- 3. Participant intends to start or discontinue a pharmacological or nonpharmacological therapy (eg, psychotherapy, sound therapy, masking, transcranial magnetic stimulation [TMS]) for tinnitus during the course of the study.
- 4. Participant has currently active and medically significant or uncontrolled hepatic, renal, cardiovascular, pulmonary, gastrointestinal, hematological, immunologic, metabolic disease (hypothyroidism with stable thyroid replacement is acceptable).
- 5. Participant's tinnitus can be modulated by maneuvers of the temporomandibular joint, head and neck, eyes, or limbs, or otherwise attributed to somatosensory cause or has had prior otoscopic surgeries or cholesteatoma.
- 6. Participants has current unilateral or bilateral hearing loss of 30 dB or greater (mild hearing loss) in one or more tested frequencies (500 Hz, 1000 Hz, 2000 Hz, and 4000 Hz), 60 dB or greater at 6000 Hz and 8000 Hz, asymmetry of 30 dB or greater in two or more tested frequencies or uses a cochlear implant or hearing aid.
- 7. Participant has history of chronic otitis media (>3 per year during past 5 years).
- 8. Participant has a total score of 15 or greater (ie, moderately severe) on the Patient Health Questionnaire-9 (PHQ-9) at Screening.
- 9. Participant has diagnosis of moderate or severe substance use disorder (excluding nicotine dependence) within 12 months of Screening, has a positive screen for drugs of abuse including tetrahydrocannabinol (THC) on Day 1 prior to dosing, or has a positive screen for alcohol on Day 1 prior to dosing.
- 10. Participant has a known allergy to progesterone, allopregnanolone, or any IP excipient.
- 11. Female participant has a positive pregnancy test or a confirmed pregnancy at Screening or prior to dosing on Day 1
- 12. Participant has had exposure to another investigational drug or device within 30 days or 5 half-lives of the investigational drug, whichever is longer, prior to the Day 1 visit.

- 13. Participant has a history of suicidal behavior within 2 years or answers "YES" to Questions 3, 4, or 5 on the C-SSRS at Screening or at Day 1 or is currently at risk of suicide in the opinion of the investigator.
- 14. Participant has donated 1 or more units (1 unit = 450 mL) of blood or experienced acute loss of an equivalent amount of blood within 60 days prior to Day 1.
- 15. Participant has any condition, comorbidity, or lifestyle consideration that in the opinion of the investigator would limit or interfere with the participant's ability to complete or partake in the study.
- 16. Participant is unwilling or unable to comply with study procedures and the required training during the Baseline Period. The participant must complete 10 VAS assessments remotely prior to Day 1.
- 17. Participant is unable to complete participation in the study, eg, due to preplanned event including elective surgery.
- 18. Participant is investigative site personnel, sponsor personnel, or a member of their immediate families (spouse, parent, child, or sibling whether biological or legally adopted).

Investigational Product, Dosage and Mode of Administration:

Brexanolone will be administered as a single, continuous, 6-hour IV infusion, administered according to the following dosing regimen:

Time point	Day 1	Day 1	Day 1
	0 to 0.5 hours	0.5 to 1 hour	1 to 6 hours
Dose	30 mcg/kg/hour	60 mcg/kg/hour	90 mcg/kg/hour ^a

A reduction in dosage to 60 mcg/kg/hour should be considered for participants who do not tolerate 90 mcg/kg/hour. No reductions below 60 mcg/kg/hour are permitted.

Duration of Treatment:

Each participant will receive a single 6-hour intravenous infusion of brexanolone.

Statistical Methods:

A detailed description of the analyses to be performed in the study will be provided in the statistical analysis plan (SAP). The SAP will be finalized and approved prior to database lock.

General Considerations

All participant data, including those that are derived, that support the tables and figures will be presented in the participant data listings. Some data may be presented only in participant listings, whereas other data may be presented in both listings and corresponding table(s) or figure(s).

For in-clinic assessments, baseline is defined as the most recent value immediately prior to the start of IP infusion. For remote daily assessments, baseline is defined as the average of all available preinfusion values per participant.

Continuous data will be summarized, at minimum, with number (n), mean, standard deviation (SD), median, Q1, Q3, minimum, and maximum. Categorical data will be summarized, at minimum, with counts and percentages. Change from baseline is calculated as the baseline value minus the post-baseline value, unless defined otherwise for specific assessments and/or endpoints.

Summary tables will generally summarize values at each timepoint and change from baseline at each post-baseline time point.

Analysis Sets
Efficacy Set
The Efficacy Set will be defined as all participants who received any amount of IP and have at least
one post-baseline efficacy evaluation.
Safety Set
The Safety Set is defined as all participants who received any amount of IP.
Statistical Methods
Statistical methods will be described in detail in the statistical analysis plan (SAP).
Descriptive statistics will be generated for safety, efficacy, and data; participant listings will be
provided in all cases.
Adverse events will be coded using Medical Dictionary for Regulatory Activities (MedDRA®). At
minimum, TEAEs will be displayed by System Organ Class and preferred term. Vital signs, clinical
laboratory measures, ECG, data will be summarized. Out-of-range safety
endpoints may be categorized as low or high, where applicable.
•

 Table 2:
 Schedule of Assessments: Screening Period

Study Procedure	Screening Period														
	Clinic Assessments	Remote Assessments													
Visit Day	-28 to -8	-7	-6	-5	-4	-3	-2	-1							
Clinic Visit	X														
Remote		X	X	X	X	X	X	X							
Informed consent process	X														
Inclusion/exclusion criteria	X														
Demographics	X														
Medical history ^a	X														
Height	X														
Physical examination b	X														
Body weight	X														
Clinical laboratory assessments ^c	X														
Drug and alcohol test d	X														
Pregnancy test (WOCBP only) e	X														
Vital signs ^f	X														
12-lead ECG ^g	X														
			 												
Audiology Diagnostics i	X														
															
VAS loudness and annoyance j		X	X	X	X	X	X	X							

Study Procedure	Screening Period														
	Clinic Assessments	Remote Assessments													
Visit Day	-28 to -8	-7	-6	-4	-3	-2	-1								
Clinic Visit	X														
Remote		X	X	X	X	X	X	X							
Remote Assessment Reminderk		X	X	X	X	X	X	X							
Participant training ¹	X														
Adverse events m				X											
Prior/concomitant medications ⁿ				X											
Nonpharmacological interventions o				X											

Abbreviations: ; ; ECG = electrocardiogram; ; ETMS = transcranial magnetic

; TMS = *t*ranscranial magnetic stimulation;

VAS = Visual Analogue Scale; VAS-A = VAS annoyance; VAS-L = VAS loudness; WOCBP = women of childbearing potential.

Note: Clinic-based screening assessments must occur within 28 days prior to IP administration and results must be reported by Day -8.

Note: When scheduled at the same timepoint, assessments will be performed in the following order: vitals, VAS,

^a Tinnitus-related medical history will be obtained by structured interview.

^b Full physical examination at Screening. Symptom-directed physical examination may be conducted at subsequent time points.

^c Safety laboratory tests will include hematology, serum chemistry, and urinalysis at all scheduled time points. Coagulation to be assessed at Screening only.

^d Drug and alcohol testing will occur at Screening (see Section 12.1.6 or a list of analytes). Drug testing will be on a urine specimen via urine dipstick. Alcohol use will be tested either on a urine specimen dipstick or breath test. A failed Screening drug or alcohol test does not exclude participation in the study if test is negative at Day 1.

^e Serum pregnancy test at screening.

 $^{^{\}rm f}$ Vital signs to include temperature ($^{\circ}$ C), respiratory rate, heart rate, and blood pressure. Heart rate and blood pressure to be collected in semi-inclined position.

g ECGs must be performed after the participant has been in a supine position for at least 5 minutes.

ⁱ A full audiological examination will be conducted at Screening including pure tone audiogram. The audiologist will perform a physical exam of ears and obtain clinical history to evaluate duration and quality (whether unilateral/bilateral, pulsatile/non-pulsatile). A healthcare professional trained to perform movement tests will evaluate whether tinnitus can be attributed to a somatosensory cause.

^j Ratings for both VAS-L and VAS-A will be done twice daily, once each in the morning and evening, on Day -7 through Day -1.

^k The participant will be contacted by the site on Day -7 through Day -1 to remind them to begin remote assessments.

¹ Participants will be trained by study personnel on the procedures for all remote assessments.

^mA phone call to follow up on any AE(s) will be conducted, if deemed appropriate by the investigator, to review the current status of the participant.

ⁿ To include all medications taken within 60 days, all psychotropic medications taken within 6 months, and all medications used to treat tinnitus regardless of timing. Participants will be asked about any changes during clinic visits.

^o Nonpharmacological interventions: eg, psychotherapy, sound therapy, masking, TMS. Participants will be asked about changes during clinic visits.

Table 3: Schedule of Assessments – Treatment Period and Follow-up Period

				Tı	reatme	nt Per	iod									
Study Procedure	Clinic Treatment Visit															EOS Visit ^a
Visit Day						2	3	4	5	6	7 ±1					
Hour From Start of Infusion	Pre- dose ^b	0	0.5	1	2	3	4	5	6	8						
Clinic Visit				•	2	X	•			•						X
Remote											X	X	X	X	X	
Clinical laboratory assessments ^c																X
Pregnancy test (WOCBP only) d	X															X
Weight	X															
Vital signs ^e	X		X	X	X	X	X	X	X	X						X
Drug and alcohol test f	X															
12-lead ECG g																X
VAS loudness and annoyance j	X		X	X	X	X	X	X	X		X	X	X	X	X	X
VAS loudness and annoyance j	X		X	X	X	X	X	X	X		X	X	X	X	X	

				Tr	eatme	nt Per	iod				Follow-up Period							
Study Procedure		Clinic Treatment Visit														EOS Visit ^a		
Visit Day	7					1					2	3	4	5	6	7 ±1		
Hour From Start of Infusion	Pre- dose ^b	0	0.5	1	2	3	4	5	6	8								
Clinic Visit	t				2	K										X		
Remote											X	X	X	X	X			
Safety phone call													X					
Remote Assessment Reminder ¹											X	X	X	X	X			
Continuous pulse oximetry m					2	X									•	•		
IP infusion					2	X												
Admission to clinic	X																	
Discharge from clinic °										X								
Adverse events p		X																
Prior/concomitant medications q		X																
Nonpharmacological interventions r		X																
Abbreviations:				;							;							

TMS = transcranial magnetic stimulation; VAS = Visual Analogue Scale; VAS-A = VAS annoyance; VAS-L = VAS loudness; WOCBP = women of childbearing potential.

; ECG = electrocardiogram; EOS = End of Study; IP = investigational product;

Note: For Day 1 assessments, assessments at 0.5 and 1 hour must be collected within 10 minutes prior to the dose increase. Assessments at timepoints 2, 3, 4, 5, 6, and 8 hours may be completed within ± 10 minutes of the scheduled time point.

Note: Preferred order of assessments at all timepoints: , VAS-L, VAS-A, vital signs (temperature [°C], respiratory rate, heart rate, and blood pressure),

- ^a The EOS Visit will be conducted at the time of discontinuation if this occurs at any time before Day 7±1 day.
- ^b All predose assessments must be completed prior to IP administration.
- ^c Safety laboratory tests will include hematology, serum chemistry, and urinalysis at all scheduled time points.
- ^d Urine pregnancy test at all scheduled time points.
- ^e Heart rate and blood pressure to be collected in semi-inclined position at all scheduled time points. Predose (Hour 0) vital signs will be collected within 60 minutes prior to dosing.
- f Drug and alcohol testing will occur prior to dosing on Day 1(see Section 12.1.6 for a list of analytes). Drug testing will be on a urine specimen via urine dipstick. Alcohol use will be tested either on a urine specimen dipstick or breath test. Participants with a failed drug or alcohol test on Day 1 are excluded from participation in the study.
- g ECGs must be performed after the participant has been in a supine position for at least 5 minutes.

for both VAS-L and VAS-A will be done twice daily, once each in the morning and evening, on Day 2 through Day 6 and on the morning of Day 7.

The participant will be contacted by the site on Day 2 through Day 6 to remind them to begin remote assessments.

^mContinuous pulse oximetry to occur for the duration of the infusion. Oxygen saturation should be recorded prior to dose escalation at 0.5 hour and 1 hour. Otherwise, it need only be recorded in the event of confirmed hypoxia, in which case, the event is to be recorded as an AE.

^o If deemed medically appropriate by the investigator, participants will be released from the clinic after the 2-hour safety assessments have been completed. Participants will be cautioned against engaging in potentially hazardous activities requiring mental alertness, including driving, until any sedative effects have dissipated A designated companion must drive the participant when they are discharged from the clinic.

- ^p A phone call to follow up on any AE(s) will be conducted, if deemed appropriate by the investigator, to review the current status of the participant.
- ^q All changes to any medication should be captured. Participants will be asked about any changes during clinic visits.
- ^r Nonpharmacological interventions: eg, psychotherapy, sound therapy, masking, TMS. Participants will be asked about any changes during clinic visits.

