7. INVESTIGATIONAL PLAN

7.1. Overall Study Design

This is an open-label study to evaluate the safety, tolerability, , and efficacy of brexanolone in adults with tinnitus following a single 6-hour continuous IV infusion. The study design is presented in Figure 2.

Figure 2: Study Design

This study includes a Screening Period of up to 28 days, a 1-day Treatment Period, and a 6-day Follow-up Period. After providing informed consent, participants will undergo screening assessments as outlined in Table 2 to determine eligibility.

Screening Period:

The Screening Period begins with the signing of the informed consent form (ICF). Eligible participants will complete additional eligibility and baseline assessments as specified in the Schedule of Assessments (Table 2).

Starting 7 days before administration of investigational product (IP) (Day -7), participants will have twice daily remote predose assessments as indicated in Table 2. Participants will receive training on how to perform all remote assessments during Screening. The participant will be contacted by the site on Day -7 through Day -1 to remind them to begin remote assessments. Assessments will be performed remotely by the participant on Day -7 through Day -1. Ratings for both VAS-L and VAS-A will be done twice daily, once each in the morning and evening.

Participants will be excluded from dosing if they do not successfully perform at least 10 of the 14 remote VAS assessments.

Clinical Protocol 547-TRM-201, Version 3.0

Treatment Period:

A continuous, 6-hour IV infusion of IP will be administered at the Clinic Treatment Visit on Day 1. Assessments will be performed as indicated in Table 3.

The participant will spend approximately 9 hours in the clinic on Day 1: 1 hour for setup of IV pump and assessments performed prior to administration of IP, 6 hours for the IP infusion, and 2 hours for safety observation at the conclusion of the IP infusion. At the discretion of the investigator, participants may stay in the clinic overnight after the end of infusion.

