13.5. Efficacy Analysis

Efficacy analyses will primarily be based on the Efficacy Set.

The two secondary endpoints of this study are (a) tinnitus perception during brexanolone infusion based on the VAS and (b) tinnitus perception after brexanolone infusion based on VAS. For remote assessments, ratings for both VAS-L and VAS-A will be obtained twice daily, once each in the morning and evening, during the both the Screening Period and on Day 2 to Day 7.

The daily arithmetic means of remote VAS-A and VAS-L ratings obtained during the Screening Period will be computed and used descriptively. The daily arithmetic means of remote VAS-A and VAS-L ratings obtained on Days 2-7 will be used both descriptively and in statistical modeling.

Each component of VAS for tinnitus will have change from baseline score (see Section 13.3 for a description of appropriate baseline for a given schedule of assessment timepoint) at each postbaseline assessment (whether during brexanolone infusion or post-brexanolone infusion) computed. Descriptive statistics of both VAS component scores and VAS component change from baseline scores will be summarized.

Each VAS component score will be analyzed separately for each secondary endpoint. This will be done separately for Day 1 (ie, during treatment) and Days 2 to 7 (ie, after treatment). The during-infusion Day 1 VAS component data will consist of VAS components obtained at 0.5, 1, 2, 3, 4, 5, and 6 hours. The post-infusion Days 2 to 7 VAS component data will consist of daily arithmetic component means.

Each analysis will utilize a mixed effects model for repeated measures. Each repeated measures model will include (a) the change from baseline score of the appropriate VAS component as the dependent variable and (b) both baseline VAS component value and visit as fixed effect independent variables. Participants will be treated as random effects.

Model- based point estimates (ie, least squares means, their 95% confidence intervals, and associated p-values) at each time point (visit) will be reported where applicable. Line plots of change from baseline scores will be plotted with standard error bars. Additional analyses will be detailed in the SAP.

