Scale; VAS-A = VAS annoyance; VAS-L = VAS loudness; WOCBP = women of childbearing potential.
Note: For Day 1 assessments, assessments at 0.5 and 1 hour must be collected within 10 minutes prior to the dose increase.
Assessments at timepoints 2, 3, 4, 5, 6, and 8 hours may be completed within ±10 minutes of the scheduled time point.
Note: Preferred order of assessments at all timepoints: VAS-L, VAS-A, vital signs (temperature [°C], respiratory rate, heart
rate, and blood pressure),
^a The EOS Visit will be conducted at the time of discontinuation if this occurs at any time before Day 7 ±1 day.
^b All predose assessments must be completed prior to IP administration.
^c Safety laboratory tests will include hematology, serum chemistry, and urinalysis at all scheduled time points.
d Urine pregnancy test at all scheduled time points.
e Heart rate and blood pressure to be collected in semi-inclined position at all scheduled time points. Predose (Hour 0) vital signs will
be collected within 60 minutes prior to dosing.

^f Drug and alcohol testing will occur prior to dosing on Day 1(see Study Protocol Section 12.1.6 for a list of analytes). Drug testing will be on a urine specimen via urine dipstick. Alcohol use will be tested either on a urine specimen dipstick or breath test. Participants with a failed drug or alcohol test on Day 1 are excluded from participation in the study.

⁹ ECGs must be performed after the participant has been in a supine position for at least 5 minutes.

for both VAS-L and VAS-A will be done twice daily, once each in the morning and evening, on Day 2 through Day 6 and on the morning of Day 7.

The participant will be contacted by the site on Day 2 through Day 6 to remind them to begin remote assessments.

^m Continuous pulse oximetry to occur for the duration of the infusion. Oxygen saturation should be recorded prior to dose escalation at 0.5 hour and 1 hour. Otherwise, it need only be recorded in the event of confirmed hypoxia, in which case, the event is to be recorded as an AE.

- old feemed medically appropriate by the investigator, participants will be released from the clinic after the 2-hour safety assessments have been completed. Participants will be cautioned against engaging in potentially hazardous activities requiring mental alertness, including driving, until any sedative effects have dissipated. A designated companion must drive the participant when they are discharged from the clinic.

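### In an uninterrupted infusion, the ±10 minute window at Hour 6 lets the during-infusion VAS endpoint rating be taken up to 10 minutes after the planned stop

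*Protocol*

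**What the plan says.** The Day 1 columns of Protocol Table 3 are headed "Hour From Start of Infusion", so Hour 6 is a clock time counted from the start of infusion. On the treatment itself, Protocol 7.1 says: "A continuous, 6-hour IV infusion of IP will be administered at the Clinic Treatment Visit on Day 1". It divides the clinic day into set-up, then "6 hours for the IP infusion, and 2 hours for safety observation at the conclusion of the IP infusion". Table 5 (Protocol 10.5) ends the last rate step at Hour 6.

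The note under Table 3 sets two timing rules for Day 1:

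- For the early time points, "assessments at 0.5 and 1 hour must be collected within 10 minutes prior to the dose increase".
- For the later ones, "Assessments at timepoints 2, 3, 4, 5, 6, and 8 hours may be completed within ± 10 minutes of the scheduled time point".

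SAP Appendix B carries the same two rules; for the later time points, including Hour 6, assessments "may be completed within ±10 minutes of the scheduled time point".

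On the analysis side, Protocol 13.5 says: "The during-infusion Day 1 VAS component data will consist of VAS components obtained at 0.5, 1, 2, 3, 4, 5, and 6 hours". SAP 9.1 likewise treats the Hour 6 rating as one of the infusion. The two during-infusion secondary endpoints (Protocol 6, SAP 5.2) name Hour 6 and no other time point. SAP 7.4 applies no visit windowing.

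**The concern.** In an infusion that runs to plan, the pump stops at Hour 6. A window that is symmetric around Hour 6 therefore extends past the end of the treatment that the rating is meant to describe. The secondary objective concerns perception while the drug is being infused, and Hour 6 is the time point at which the plan chose to measure it.

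A rating made after the stop differs in two ways. The drug level has begun to fall, and the participant, in an open-label study, can know that the infusion is over. Both VAS questions ask about tinnitus at the moment of rating (Protocol 11.1.2), so either could bear on the answer. SAP section 12 expects about 10 dosed participants, so one rating carries about one-tenth of the Hour 6 mean.

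What is at stake is how exactly a named endpoint matches its objective. The primary safety endpoint is not affected.

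**Working it through.** The plan gives no figure to reproduce here. The check is to overlay each permitted window on the infusion, then to gauge size under stated assumptions.

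**1. Windows against the infusion** (minutes from start; uninterrupted infusion = 0 to 360)

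| Time point | Permitted window | Minutes after planned stop |
|---|---|---|
| 0.5 h | 20 to 30 | 0 |
| 1 h | 50 to 60 | 0 |
| 2 h | 110 to 130 | 0 |
| 3 h | 170 to 190 | 0 |
| 4 h | 230 to 250 | 0 |
| 5 h | 290 to 310 | 0 |
| 6 h | 350 to 370 | 370 − 360 = 10 |

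At Hour 6, 10 of 20 permitted minutes (50%) follow the planned stop. No other VAS time point classed as during-infusion is affected.

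**2. Does other text close the gap?** The preferred-order note under Table 3 puts VAS ahead of vital signs but does not tie it to the pump stop. SAP 9.1 models Day 1 by hour and has no rule for a rating made after the stop. The footnote to the VAS row of Table 3 lacks its opening in the public copy of both documents; what is legible concerns the later days.

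**3. Size in terms of drug level.** The documents give no half-life, so the values below are assumptions. With first-order decline after the stop and half-life h in minutes, k = ln 2 / h.

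- Fall for someone rated exactly 10 minutes after the stop: 1 − exp(−10k).
- Average fall over all participants, if ratings were spread evenly over the 20 minutes: half are not late, and the late ones are spread over 0 to 10 minutes. This gives 0.5 × [1 − (1 − exp(−10k)) / (10k)].

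| Assumed half-life | Fall at +10 min | Average fall, even spread |
|---|---|---|
| 0.5 h | 20.6% | 5.4% |
| 1 h | 10.9% | 2.8% |
| 2 h | 5.6% | 1.4% |
| 4 h | 2.8% | 0.7% |
| 9 h | 1.3% | 0.3% |

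Worked line for 1 h: 10k = 0.1155; 1 − exp(−0.1155) = 0.109; 0.5 × (1 − 0.1091/0.1155) = 0.028.

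**4. From level to VAS.** If a share p of participants is rated after the stop and those ratings have lost a fraction f of the effect, the mean change shrinks by p × f. The documents give neither p nor f. For illustration only, p = 0.25 with f = 0.1 gives 2.5%, and p = 0.5 with f = 0.25 gives 12.5%.

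**5. After the fix.** The Hour 6 VAS window becomes 350 to 360, and the permitted minutes after the stop fall from 10 to 0.

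**The case against.** The strongest reply is that Hour 6 is a nominal time, that ±10 minutes around it is a workable definition of an end-of-infusion rating, and that nothing in the study depends on the difference. Much of this stands.

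- **Permitted does not mean done.** A reader might infer that the endpoint does mix on- and post-infusion ratings, or that about 5 of 10 participants will be rated late. The documents support neither. The window allows late ratings without causing them, and 5 of 10 is 0.5 × 10 under an assumed even spread. The preference for VAS before vital signs may pull the rating earlier.
- **The after-infusion analysis is untouched.** A reader might infer that the plan's two VAS objectives become blurred. Protocol 13.5 and SAP 9.1 separate the analyses by day: Day 1 for during, Days 2 to 7 for after. A rating at 6 h 10 min never enters the second.
- **The 0.5 h and 1 h rule is not proof of inconsistency.** It covers all Day 1 assessments and is tied to a rate increase. Footnote m of Table 3 also asks for oxygen saturation before each escalation. A pre-escalation check explains the rule at least as well as a wish to protect the VAS. No escalation occurs at Hour 6.
- **Knowing that treatment is over** adds little. Participants know the infusion is open-label, and its length is fixed in advance, so expectation just before and just after the stop may hardly differ.
- **There is a built-in comparison.** Hours 2 to 5 lie wholly within an uninterrupted infusion, and Hour 5 has the same planned rate as the run-up to Hour 6.
- **Interrupted infusions need care.** The documents do not say whether lost time is added, so a rule tied only to the end of infusion would not always yield an Hour 6 rating. The fix has to be confined to uninterrupted infusions.

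None of this removes the basic mismatch: a rating labelled during-infusion may, within the rules, be taken after the planned stop.

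**Conclusion.** The point holds as a minor one. In an uninterrupted infusion, both documents permit the Hour 6 VAS-L and VAS-A ratings up to 10 minutes after the planned stop, while Protocol 13.5 classes them as during-infusion. The two named endpoints can therefore include some post-stop ratings.

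The timing result rests only on figures in the documents. The size does not: the number of late ratings is unknown, no half-life is given, and the effect on VAS cannot be computed. It is probably small. Under the assumed half-lives and an even spread, the average fall in drug level is about 5% at most, and drug level is not VAS. The estimate would grow only if offset were faster than assumed or if most ratings were taken late.

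This is a cheap improvement in how well the endpoint matches its objective. The documents do not support calling it an error that changes the study's conclusions: there is no comparator and no success threshold, and SAP 9.1 reports estimates across all Day 1 hours. Paused or abandoned infusions are a separate matter and are not covered here.

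**What to change.** - **Protocol Table 3 note and SAP Appendix B:** for uninterrupted infusions, require the Hour 6 VAS-L and VAS-A within the 10 minutes up to Hour 6, before the pump is stopped. Keep ±10 minutes for the other Hour 6 procedures and for interrupted infusions.
- **SAP 9.1:** where rating clock times are recorded, flag in the VAS listing any Hour 6 rating timed after the recorded infusion stop. SAP 8.7 already uses the stop time to derive exposure. The documents do not expressly say that VAS clock times are captured, so this step depends on that. If data collection is already complete, it is the part that can still be done.

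The cost is one sentence in the schedule note, one flag in a listing, and a slightly tighter window for one rating. No assessment is added, and neither the infusion nor the safety procedures change.
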